5.3 Claims of Performance

Easy to use.

Comfortable.

Faster than existing products used.

Reduces pain.

Secure dressing retention

CE-GAX001-01

V4.0

CR: 144

6 DESIGN OF THE CLINICAL INVESTIGATION

6.1 General

6.1.1 Description

Questionnaire, Pilot Trial, Single-arm, unblinded study of Hidrawear AX

6.1.2 Measures to Minimise Bias

The sponsor will not be involved in the study processes or day to day management. The sponsor has agreed to work with the Clinical Research Platform, (CRP) an independent research organisation who will conduct an independent trial. A research nurse will record the data. The Clinical Operations Manager of the CRP is [name] with an address at [name].

6.1.3 Primary and Secondary Endpoints

Primary Endpoint

• The change in the ease of use at week 3 compared to Day 0

Secondary Endpoints - Subject Assessment

- Ease of use W2 vs W1
- Comfort measured on a 10 point scale D21 vs D0
- Pain measured on a 10 point scale D21 vs D0
- Time measured on a 10 point scale D21 vs D0
- Dressing retention confidence measured on a 10 point scale D21 vs D0

Secondary Endpoints – Nurse Assessment

- Necessity to stretch/contort the body to apply dressing
- Did subject need assistance
- Could dressing be applied without raising arms over head
- Additional equipment used- mirror, scissors etc.

Outcome selection rationale:

- Assessment of ease of use as primary outcome was selected as most users have voiced frustration
- Comfort was selected as we wish to learn if Hidrawear AX is comfortable to use.
- Dressing retention confidence was selected as user have voiced frustration
- Dressing related pain was selected as HidraWear AX may reduce unnecessary patient distress due to dressing/adhesive related pain
- Time was selected as regular wound dressing changes are time consuming (6)

CE-GAX001-01

V4.0

CR: 144

DLQI was selected as it a validated tool that has been commonly used for assessment of quality of life for HS subjects. will assess if Hidrawear AX is better than the current products used by HS subjects.

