2 INTRODUCTION

Hidradenitis Suppurativa (HS) is a debilitating lifelong condition characterized by painful nodules and lesions localized mainly in the inverse body areas, such as the axillae and groin [1]. These lesions are typically fluid filled and require regular wound dressings. People with HS live in dressings and bandages.

Hidradenitis Suppurativa

- Presents after puberty with an average diagnosis pathway of 8 years [2]
- Is frequently misdiagnosed due to lack of clinical awareness [3]
- Causes deep seated, painful skin lesions, tunneling tracts and wounds
- Affects the armpits, groin, thigh and buttocks
- Causes irreversible skin damage
- Causes high levels of subject pain, distress and despair [4]
- Subjects at higher risk of anxiety, depression and suicide [5]

People living with HS are tending to their lesions widely unaided. The majority of subjects, unless referred to a wound clinic, are self-managing. [6]

There are no recommended products or guidelines on how to manage HS lesions and there are no wound dressings that are suitable for use on the armpit. Current dressings often leak, move or fall off and the constant application and removal of adhesives to the skin further irritates and damages the affected area. Subjects are doing on average 3-4 dressing changes per day, using products that are not fit for purpose.

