2.1 Description of the Investigational Device

HidraMed Solutions has developed an adhesive free wound dressing fixation device for people living with Hidradenitis Suppurativa (HS), a chronic and debilitating disease which causes non-healing lesions of the skin, mainly in the armpit, groin, thigh and buttocks - Hidrawear AX, designed to make dressing changes quick and easy for subjects.

The Hidrawear AX is designed to improve the wound care management for HS and chronic wound subjects. The unique features of the product completely remove the use of adhesives on the skin. Designed by a patient, for patients, Hidrawear AX provides comfort, ease of use and effective care for the every-day management of HS lesions.

The 3- part system is comprised of

- 1. The investigational device: the Hidrawear AX: A washable garment
- 2. An off-the-shelf dressing
- 3. An off-the-shelf mechanism to attach the dressing to the Hidrawear AX, such as a fastener supplied with the dressing or medical tape

The body conforming garment acts as a second skin and incorporates largely perforated panels over wound affected areas, minimising skin contact and aerating the area. The main function of the perforated is to act as a retaining device for the wound pads.

[figure not shown]

[figure not shown]
CE-GAX001-01

V4.0

CR: 144

The garment facilitates easy insertion, removal, precise positioning and adjustment of a non-adhesive wound dressing onto the effected wound space. The perforated section of the garment sits on the outer surface of the dressing providing provisional fixation. Next, an outer patch is placed on the outside of the garment on the footprint of the dressing. Through a hook and loop mechanism the dressing is now fully secured in place. It is designed so that quick, precise and pain free dressing changes can be achieved in less than 15 seconds

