5 OBJECTIVES AND HYPOTHESIS OF THE CLINICAL INVESTIGATION

5.1 Objectives

The objective is to evaluate the ease of use of Hidrawear AX compared to the subject's existing product use in 20 subjects with HS (Hidradenitis Suppurativa).

Secondary objectives are:

To establish the impact of wound care to patients using online survey.

To evaluate if Hidrawear AX:

- Is comfortable
- Improves quality of life
- Faster to use than the subject's existing product
- Reduces dressing related pain
- · Secure dressing retention

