5.2 Hypothesis

When compared to standard methods of dressing the axilla, Hidrawear AX will be equivalent to or superior in terms of:

Ease of use

Comfort (wearing) to user

Time to apply

Dressing related pain and discomfort

Secure Dressing retention

And in turn will have a positive impact on the patient's quality of life.

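### The speed and retention claims in section 5.3 outrun the planned data, which are ratings of perceived time burden and of confidence, with no recorded duration or structured retention-failure item

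*Combined protocol and SAP*

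**What the plan says.** Section 5.1 lists among the things to be evaluated whether the device is "Faster to use than the subject's existing product" and gives secure retention. Section 5.2 hypothesises that HidraWear AX is at least equivalent to usual methods on several attributes, including application time and "Secure Dressing retention". Section 5.3 is the assertive one: two of its five claims are "Faster than existing products used" and "Secure dressing retention".

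The corresponding secondary endpoints in section 6.1.3 are "Time measured on a 10 point scale D21 vs D0" and "Dressing retention confidence measured on a 10 point scale D21 vs D0". Section 6.1.4 confirms that subjects score both on a 10-point visual analogue scale at Day 0, for their usual product, and at Day 21, for HidraWear AX. At Day 0 the subject may either demonstrate or explain the usual method. At Day 21 the subject is asked to demonstrate, and the nurse assesses the activity at both visits.

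**The concern.** *Faster* and *secure retention* describe what the product does: a change takes less time, and the dressing stays where it was put. The endpoints record what the subject thinks about each. The two can part company. A change that hurts less or needs less contortion may feel shorter without being shorter, and confidence can rise without any count of dressings that failed. The study is single-arm and unblinded (section 6.1.1), so nothing in the design separates impression from performance.

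At stake is the wording of the conclusions. If the plan is followed exactly and both ratings improve, the report could repeat the section 5.3 claims as demonstrated when no one recorded how long a change took or how often a dressing failed. Section 7.1 also expects the pilot to supply estimates of effect and variability for a full-scale study. For these two attributes it would supply them only on the rating scales.

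**Working it through.** No arithmetic decides this. The check is to go through every appended form and ask whether it could yield a duration, or a record that a dressing leaked, shifted or came off.

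| Form | When and for which product | Time content | Retention content |
|---|---|---|---|
| Subject assessment, Appendix 3 | Day 0, usual product | Rating of time burden | Rating of confidence |
| Subject assessment, Appendix 4 | Day 21, HidraWear AX | Rating of time burden | Rating of confidence |
| Nurse assessment, Appendix 5 | Day 0 and Day 21 | None | None |
| Daily check-in, Appendix 7 | Days 1 to 21, HidraWear AX | None | None; asks temperature, dressing count and comments |
| Weekly check-in, section 6.1.4 and Appendix 7 | Days 7 and 14, HidraWear AX | Not listed in the text; the schedule in section 6.4.1 lists it with the ratings | Confidence listed in the text, not in the schedule |
| DLQI, Appendix 6 | Days 0, 7, 14 and 21 | Item 10 grades how much of a problem treatment is; not a duration | None |
| Online survey, Appendix 2 | Before the trial, existing products | Item 11: minutes per day, in bands | Item 10: ever had a failure, yes/no; item 13: confidence 0 to 10 |

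**Count for HidraWear AX in trial subjects:** duration items 0; structured retention-failure items 0. On the Day 21 form there is one time-burden rating and one confidence rating.

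**Could the synopsis mean elapsed time?** It lists time at Day 21 against Day 0 without a unit. Sections 6.1.3 and 6.1.4 and the question wording in Appendices 3 and 4 all make it a rating.

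**Could the survey fill the gap?** Section 3.1 plans a comparison with survey data, and items 10 and 11 are the protocol's own failure and duration questions. But section 6.1.4 describes the survey as a precursor that collects no identifying information. It covers existing products, so it yields neither a HidraWear AX value nor a within-subject comparison. Item 11 also includes time spent tending lesions and is per day, not per change.

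**Could failures surface elsewhere?** Possibly, through free-text comments, the daily dressing count, the check-up calls or device-deficiency records (section 15.7). None gives a rate with a defined numerator and denominator. The count has no baseline value from trial subjects and may move for reasons other than retention. Section 15.3, headed device deficiency, repeats the adverse device effect definition, so the protocol does not say whether a leak without harm is to be logged.

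**Limits of the check.** The scale graphics in Appendices 3 and 4 are not shown, and neither are the eCRF mentioned in section 8.2 nor the event records under QP025 in section 15.6. The count therefore applies to the appended forms as they can be read.

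**The case against.** The best defence is that the plan is open about what it measures. The endpoint list names a 10-point time scale and retention *confidence*, and section 6.1.3 gives a reason for each. For a home-use product, the user's view of burden and security is a proper outcome. By Day 21 confidence rests on three weeks of wear. The study is a feasibility pilot without a power calculation, and both endpoints are secondary. All of this stands. It rules out saying that the endpoints are invalid and limits the weight of the point.

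A reader might infer more than the documents support in three ways.

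- *That section 5 as a whole states speed and retention as facts.* It does not. Section 5.1 sets out to evaluate and section 5.2 is a hypothesis; only section 5.3 is assertive. Nothing there says that this pilot alone must establish the claims.
- *That the study fails to test the duration in section 2.1*, where the protocol says: "It is designed so that quick, precise and pain free dressing changes can be achieved in less than 15 seconds". That describes design intent. It is not an objective, hypothesis, section 5.3 claim or endpoint, and section 4.6 refers separately to verification and validation testing of the garment.
- *That the gap can be sized by multiplying out the rate in section 2*, "Subjects are doing on average 3-4 dressing changes per day". That figure describes existing products and is not specific to the axilla, and section 6.4.2 notes that subjects are often affected at several sites. It does not give a number of HidraWear AX changes.

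**Conclusion.** The point holds as a mismatch between two claims and the data planned for them. Two of the five claims in section 5.3 are worded as product performance, while the appended forms provide one perception rating for each and no direct measurement. Followed exactly, the plan can support *perceived as less time consuming* and *greater confidence in retention*. It cannot show that a change takes less time or that dressings stay in place.

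This rests on the appended forms being the full set of trial instruments for these attributes, and on the unseen scale graphics being rating scales, as the text describes them. If the eCRF holds a duration or a structured failure item, the point falls for that attribute. The primary endpoint is untouched. It is worth correcting because the correction is cheap, not because the study depends on it.

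**What to change.** **Minimum.** Limit the two section 5.3 claims and the report's conclusions to *perceived as less time consuming* and *greater confidence in retention*. For the report this costs only wording. Changing section 5.3 is an amendment needing ethics committee approval first (sections 10 and 13.1).

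**Alternative, if the claims are to be kept as worded:** obtain measured data at contacts that already exist.

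1. Add a start-to-finish duration field to the Day 0 and Day 21 nurse forms. Define start and finish identically for both products, including whether putting on the garment counts. Report paired times descriptively for subjects who demonstrate at both visits, and state how many only explained at Day 0. Keep the 10-point rating as the endpoint for all subjects.
2. Add two yes/no items to the daily check-in: whether any dressing leaked, shifted or came off in the past 24 hours, and whether HidraWear AX was worn. Report the failure-day rate descriptively, with an interval that allows for clustering of days within subject and stays within 0 to 100%. Report the number of unanswered check-ins beside it.

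**Costs and limits.** An approved amendment and slight extra subject burden, but no added staff or visits. Pairing will be incomplete and possibly selective, because the usual method may be explained rather than shown and section 4.4 warns that demonstrating it may cause discomfort. Both measures remain unblinded. The failure rate would have no own-product comparator, so it would describe HidraWear AX without supporting a comparative retention claim.

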6.1.4 Methodology

Before the study commences on site, a survey will be shared into select closed patient groups online, to capture the patient experience of living with Hidradenitis Suppurativa (HS) in terms of self-managing wound care and the impact that HS wound care has on patients' day to day life, physically, financially and emotionally.

A secure and confidential survey tool (Typeform) will be used. This is governed under EU data legislation and encrypted to ensure privacy. The survey will not collect any identifying information and is a precursor to the HidraWear AX Pilot Study.

Day 0

Subjects will visit trial site or have a home visit from research nurse.

Following consent and enrolment, Subjects will be asked to demonstrate or explain their usual method of dressing their wound using their usual wound dressing products.

Subjects will assess this activity based on ease of use, comfort, experienced pain, confidence in dressing retention and time, using a 10 point visual analogue scale. (see appendix 2)

The subjects will complete a Dermatology Quality of Life Index Survey. (see appendix 5)

The research nurse will assess the activity based on whether the subject needs assistance, uses additional equipment, contorts or stretches their body, can dress the wound without raising their arms above their head. (See appendix 4)

Day 1-21

Daily Check in with Subjects:

Each day, at 1pm, subjects will receive an email requesting them to check in with the researcher by answering 3 questions.

- 1. What is your temperature?
- 2. How many dressings did you use in the last 24 hours?
- 3. Any comments?

This check in should take less than 5 minutes to complete.

Subjects will be required to respond by 5pm each evening. If subject has not responded by 5pm, a reminder text message will be sent to them.

If subject does not respond within 24 hours, the research nurse will call the subject to check in and take answers over the phone.

CE-GAX001-01

V4.0

CR: 144

Weekly Check in with Subjects:

On day 7 and 14 subjects will be asked to complete the Dermatology Quality of life survey and questions on Ease of use, comfort, pain and confidence, at home. A link to the surveys will be emailed to them at 1pm in the afternoon with their daily check in.

Subjects will be required to respond by 5pm each evening. If subject has not responded by 5pm, a reminder text message will be sent to them.

If subject does not respond within 24 hours, the research nurse will call the subject to check in and take answers over the phone.

Day 21

Subjects will return to site or be visited by research nurse for review.

Subjects will be asked to demonstrate how they dress their wound using HidraWear AX.

Subjects will assess this activity based on ease of use, comfort, experienced pain, confidence in dressing retention and time, using a 10 point visual analogue scale. (see appendix 3)

The subjects will complete a Dermatology Quality of Life Index Survey. (see appendix 5)

The research nurse will assess the activity based on whether the subject needs assistance, uses additional equipment, contorts or stretches their body, can dress the wound without raising their arms above their head. (See appendix 4)

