4.4 Risks Associated with Participation in the Clinical Investigation

On Day 0, the subject will be asked to demonstrate or explain dressing their axilla using their usual methods and products. These products may use adhesives and in turn cause discomfort to subjects during demonstration.

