6.4 Procedures

6.4.1 Pilot Study Procedures

Procedures & Assessments	Day 0	Day	Day	Day	Day	Day	V2;
	Enrolment	1 - 6	7	8 - 13	14	15 - 20	End of
	Assessment						Intervention
							Day 21
Informed Consent	X						
Medical / HS History	X						
Armpit Clinical assessment	X						X
Inclusion/exclusion criteria	Х						
Observe Subject using usual method of dressing wound	Х						
Dermatology Quality or life index survey, Ease of Use, Comfort, Time, Pain scale.	Х		Х		Х		Х
Subject trained on use of HidraWear Ax	Х						
Subject trained on use of Thermometer	Х						
Subject daily use of Hidrawear AX		Х	Х	Х	Х	Х	X
Temperature Record	Х	Х	Х	Х	Х	Х	Х
Observe Subject using Hidrawear AX							X
Daily Survey		Х	Х	Х	Х	Х	Х
Checkup phone call			Х		Х		
Researcher Data Entry	Х	Х	Х	Х	Х	Х	Х
Adverse Events	Х	Х	Х	Х	Х	Х	Х

CE-GAX001-01

V4.0

CR: 144

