10. Have you ever had a dressing leak/move or fall off? Yes/No

11. How long do you typically spend doing dressing changes and tending to your lesions on a daily basis?

0-5	6-10	11-15	16-20	21-25	26-30	31-35	36-40	41-45	Over 45
minutes									

- 12. Do you think that your wound care needs are being met by current dressing options? Yes/no/maybe (please elaborate)
- 13. How satisfied are you with current dressings in terms of

Comfort - scale 0-10

Ease of application, adjustment and removal (a full dressing change) – scale 0-10

Confidence it won't leak, move or fall off scale 0-10

- 14. Do you believe that wound care / dressing changes are a contributing factor to a reduced quality of life for you? Yes/No/Don't Know
- 15. Does managing your wounds / dressings impact negatively on:

Work life yes/no Social life and hobbies yes/no Sex and relationships yes/no Day to day activities yes/no Mental health yes/no Financial well being yes/no

General wellbeing yes/no

16. Please tell us, in your own words about your experiences of home management/ dressings for HS. How does it make you feel?

For example- What is your biggest frustration with dressings? Does it impact your daily life? Any problems you experience when doing your dressing changes. Do you need a mirror, extra equipment, assistance? What is the worst part about it and how do you manage on a daily basis?

Section 4: HS information and Support

CE-GAX001-01

V4.0

CR: 144

1. Where do you find your information on HS?

Doctors/	Information	Online patient	Meeting other	Other (please
Healthcare Websites		forums/groups	patients	specify in
				comment)

2. What do you think would help you feel more supported in managing your HS? What would you like to see? Please elaborate in comments.

Thank you for participating in our survey. Your time and effort will directly contribute to the publication that highlights the daily impact of HS wounds and wound care on the patient's life.

If some of the questions have made you feel upset about your HS, please visit the following sites for information and support:

https://irishskin.ie/ask-our-dermatology-nurse/

https://hopeforhs.org/

CE-GAX001-01

V4.0

CR: 144

21 APPENDIX 3 – SUBJECT ASSESSMENT FORM DAY 0

Subject Assessment Day 0

[figure not shown]
Please dress your wound using your usual product and method.

While you are dressing your wound, please pay close attention to the following:

[figure not shown]
- How easy/difficult it is

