- Is it time consuming for a full dressing change
- How comfortable/uncomfortable is a dressing change
- Do you experience dressing related pain
- How confident are you that your dressing will not leak or move.

Once the dressing change is complete, please answer the following:

1. Is it easy/difficult to change your dressing using your current product and method? Please indicate the level of difficulty involved.

2. How time consuming is a dressing change using your current product and method?

Page 45 of 56

[figure not shown]
The Master Copy of this document is electronically approved and maintained as an electronic record

CE-GAX001-01 V4.0

CR: 144

[figure not shown]
3. How Comfortable is it to use and wear your current dressing?

4. Do you require pain killers before a dressing change? Please tick

Yes	No

5. Do you experience dressing related pain using current product?

[figure not shown]

CE-GAX001-01

[figure not shown]
V4.0

CR: 144

6. How confident are you that your current dressing will not leak or move?

7. How confident do you feel in yourself about your body image – self confidence/self esteem?

CE-GAX001-01

V4.0

CR: 144

22 APPENDIX 4 – SUBJECT ASSESSMENT FORM DAY 21

[figure not shown]
Please dress your wound using HidraWear AX

While you are dressing your wound, please pay close attention to the following:

[figure not shown]
- How easy/difficult it is
- Is it time consuming for a full dressing change
- How comfortable/uncomfortable is a dressing change
- Do you experience dressing related pain
- How confident are you that your dressing will not leak or move.

Once the dressing change is complete, please answer the following:

8. Is it easy/difficult to change your dressing using HidraWear AX? Please indicate the level of difficulty involved.

9. How time consuming is a dressing change using HidraWear AX?

Page 48 of 56

The Master Copy of this document is electronically approved and maintained as an electronic record

[figure not shown]

CE-GAX001-01

V4.0

CR: 144

[figure not shown]
10. How Comfortable is it to use and wear HidraWear AX?

11. Do you require pain killers before a dressing change? Please tick

Yes	No		

12.
Do you experience dressing related pain using HidraWear AX?

[figure not shown]

CE-GAX001-01

[figure not shown]
V4.0

CR: 144

13. How confident are you that HidaWear AX will not leak or move?

14. How confident do you feel in yourself about your body image – self confidence/self esteem?

CE-GAX001-01

V4.0

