23 APPENDIX 5 – NURSE ASSESSMENT FORMS

Nurse Assessment Day 0

Subject Number:	
,	

Subjects use of usual product and method for dressing a wound.		
What dressings did subject use?		
	Yes	No
Did subject contort/ stretch to apply dressing?		
Did Subject need assistance?		
Could subject apply dressing without raising arms over their head?		
Did subject use additional equipment to dress their wound? eg. Scissors, pins, tape, mirror		
If yes, please specify		

CE-GAX001-01

V4.0

CR: 144

Nurse Assessment Day 21

Subject Number:	

Subjects use of HidraWear AX for dressing a wound.		
Did subject contort/ stretch to apply dressing?		
Did Subject need assistance?		
Could subject apply dressing without raising arms over their head?		
Did subject use additional equipment to dress their wound? eg. Scissors, pins, tape, mirror		
If yes, please specify		

CE-GAX001-01

V4.0

CR: 144

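### Day 0 may be explained rather than performed, but the schedules and forms assume a performed dressing change and no printed form records which happened

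*Combined protocol and SAP*

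**What the plan says.** Two places allow either mode at Day 0. Section 6.1.4 states: "Subjects will be asked to demonstrate or explain their usual method of dressing their wound using their usual wound dressing products". Section 4.4 states: "On Day 0, the subject will be asked to demonstrate or explain dressing their axilla using their usual methods and products", and then warns: "These products may use adhesives and in turn cause discomfort to subjects during demonstration".

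The other places describe a change that is carried out:

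- The schedule in section 6.4.1 lists "Observe Subject using usual method of dressing wound" at Day 0, and the schematic in Appendix 1 has the same row. Neither mentions explaining.
- The Day 0 subject form (Appendix 3) instructs: "Please dress your wound using your usual product and method". It introduces the ratings with "Once the dressing change is complete, please answer the following".
- The Day 0 nurse form (Appendix 5) asks, with Yes/No columns, about stretching, assistance, arm raising and extra equipment. One item reads "Could subject apply dressing without raising arms over their head". It also has free text for the dressings used and the equipment.
- For Day 21, section 6.1.4 says only: "Subjects will be asked to demonstrate how they dress their wound using HidraWear AX".

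Section 6.1.3 makes the ease-of-use change from Day 0 to week 3 the primary endpoint and lists the four nurse items as secondary endpoints. Section 6.2 says the comparator, the subject's own product, is assessed at week 0.

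**The concern.** A nurse who follows section 6.1.4 may accept a verbal account and must then complete a form designed for observation. Whether the subject stretched or raised her arms cannot be seen in an explanation, and assistance and equipment become self-report. The form has no way to say so. The subject's own Day 0 ratings of ease, pain and time would also rest on an account, whereas the Day 21 ratings follow a change just performed.

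The usual product is assessed within subject only at Day 0 of a single-arm, unblinded study, so no later reading can expose or correct a mixed baseline. Section 6.1.2 relies on an independent organisation and nurse-recorded data to limit bias, which does not help where the nurse saw nothing. Section 7.1 intends the data to supply effect and variability estimates for a full-scale study, so an unrecorded mixture would carry forward.

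The mode may also not be random. Given the warning in section 4.4, the subjects with most discomfort from adhesive products could be the ones who explain. That is a possibility, not something the documents show.

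**Working it through.** There is no figure in the plan to reproduce on this point. The contradiction is one of text, and the arithmetic only gives it a scale.

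**Passages side by side**

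| Place | Day 0 mode |
|---|---|
| 6.1.4 and 4.4 | performed or explained |
| 6.4.1 and Appendix 1 | observed using the usual method |
| Appendix 3 | performed, then rated |
| Appendix 5 | Yes/No on what happened; no mode field, no not-observed option |
| 6.1.4, Day 21 | performed only |

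**Inputs.** From the documents: 23 subjects (7.2) and up to 6 drop-outs (6.3.6, 7.4), so 23 − 6 = 17 if none is replaced. Assumed, because the documents give no values: share explaining *f* = 20–50%; difference *d* between an explained and a performed rating = 1–2 points in either direction; SD of the change = 2.5 points.

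**Nurse items on stretching and arm raising.** An explained-only subject's true Day 0 answer could be Yes or No, so each leaves the Yes-proportion undetermined by 1/n:

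- n = 23: 1/23 = 4.3 percentage points
- n = 17: 1/17 = 5.9 percentage points

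Over all subjects the undetermined width equals *f*, that is 20–50 points at the assumed shares. This bound needs no assumption about direction.

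**Primary endpoint.** Bias in the mean Day 0 rating, and hence in the mean change, has size *f* × *d*:

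- 0.2 × (±1) = ±0.2
- 0.3 × (±2) = ±0.6
- 0.5 × (±2) = ±1.0
- *f* = 0 gives 0

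For comparison, the standard error of the mean change is 2.5/√23 = 0.52, or 2.5/√17 = 0.61.

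**Pairs observed at both visits.** Of 23: 23 × 0.8 = 18.4 and 23 × 0.5 = 11.5. Of 17: 17 × 0.8 = 13.6 and 17 × 0.5 = 8.5. The 95% half-width for a 50% proportion, 1.96 × √(0.25/n), is:

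| n | 23 | 18 | 12 | 8 |
|---|---|---|---|---|
| Half-width | 0.20 | 0.23 | 0.28 | 0.35 |

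These half-widths are for a single proportion by normal approximation. They show the order of the precision loss, not the exact interval for a paired comparison.

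**The case against.** The strongest reply is that the effect may be small or absent. Subjects follow Appendix 3, which tells them to dress the wound, so few or none may explain. Several rating items ask about general experience with the current product, and the introduction puts average dressing changes at 3–4 a day, so an explainer would probably be rating a recent change. This stands in part: for the subject ratings the contrast is one of degree, the bias has no known direction, and it is zero if everyone performs. The assumed 20% lower share has no support in the documents.

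The online survey also rates current dressings on 0–10 scales, and section 3.1 names it as a comparison. But it is anonymous and precedes the study, so it offers at most a group-level check and no within-subject comparator.

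A nurse could annotate the free text or leave items blank. Nothing asks her to record the mode, however. Source records outside the protocol, and figures missing from the Appendix 3 pages, cannot be checked; the claim is limited to the printed forms.

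Section 6.3.6 plans replacement of drop-outs from a waiting list, so the figures for 17 apply only if that fails.

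Finally, explaining may be a deliberate accommodation, and this is a feasibility-sized pilot without a power calculation. Both are fair points. They argue for keeping explanation available and for a light remedy, not for leaving the passages in conflict or the mode unrecorded. Improving the design is one of the pilot's stated purposes in section 7.1.

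**Conclusion.** The concern holds and should be fixed. The contradiction and the missing mode field are certain from the text. Followed as written, section 6.1.4 allows an explanation to be stored as a nurse observation in four secondary endpoints, and the printed forms could not identify those records later.

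The nurse items are hit most: 4.3 percentage points undetermined per explained-only subject with 23 subjects, 5.9 with 17. For the primary endpoint, 0.2 to 1.0 points either way is an illustration under the assumed shares and shifts. The upper end exceeds the standard error of the mean change at the assumed SD. The actual direction and size cannot be determined from the documents, and the effect is nil if nobody explains.

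**What to change.** 1. Reconcile sections 6.1.4 and 4.4 with Appendix 3 and both schedules, with a performed change as the default and explanation kept as a recorded exception.
2. Add a tick-box (performed / explained only) to both Day 0 forms, and a not-observed option to the nurse items.
3. Compare nurse items at Day 21 with Day 0 only in subjects observed at both visits, and state that number.
4. Keep the all-subject ease-of-use change as the main result; beside it, report the same summary for subjects who performed at Day 0 as a sensitivity analysis.
5. Report how many subjects explained, and their Day 0 ratings.

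The direct cost is one tick-box on two forms, one response option, wording edits and one extra summary. There are two downsides. Nurse pairs fall, at the assumed shares, to about 18 down to 11–12 of 23, or 13–14 down to 8–9 of 17, with the precision loss shown above. And the performed-only subset may be selected if subjects with most discomfort tend to explain, which is why the all-subject result stays the main one and the explainers are described. If the sponsor prefers a different default at Day 0, recording the mode and stating how explained-only records are analysed still cures the main defect.
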